## **2.2 Primary Hypothesis**

The primary hypothesis is that a multi-component technology-mediated intervention (Roadmap 2.0) with focus on the positive aspects of caregiving will improve caregiver HRQOL.

## **2.3 Study Objectives**

### **2.3.1 Primary Objective**

The primary objective is to test the statistical significance or difference between the “treatment” (Roadmap 2.0) arm and the control (usual care) arm in the measured outcome of caregiver HRQOL, assessed by the PROMIS Global Health scale, at day 120 post-HCT.

### **2.3.2 Exploratory Objectives**

- 2.3.2.1 Caregiver and patient HRQOL, as assessed by the following PROMIS measures: Global Health, Profile 29+2 and 25, Companionship, Self-Efficacy for Managing Symptoms, Self-Efficacy for Managing Daily Activities, Positive Affect and Well-Being, and Emotional Support.
- 2.3.2.2 Caregiver and patient HRQOL, as assessed by the Perceived Stress Scale.
- 2.3.2.3 Caregiver and patient HRQOL, as assessed by the Resilience, Optimism and Gratitude scales
- 2.3.2.4 Patient (ages 8-17 years) and parent proxy for pediatric patients (ages 5-17 years) HRQOL, as assessed by measures of PROMIS sleep disturbance and Profile 25.
- 2.3.2.5 Caregiver and patient negative and positive dyadic interaction, as assessed by measures of the Dyadic Relationship Scale.
- 2.3.2.6 Caregiver and patient physical activity through physiological data capture using the wearable sensors.
- 2.3.2.7 Caregiver and patient health care utilization data (e.g., total count of hospital days, readmissions, and ambulatory care clinic visits).

- 2.3.2.8 Overall patient survival during first 120 days' post-HCT.
- 2.3.2.9 Obtain user experience of the Roadmap 2.0 app through the Mobile Application Rating Scale (MARS) and qualitative interviews.

## **2.4 Participant Eligibility**

Subjects must meet all of the eligibility criteria to be enrolled to the study. Study intervention may not begin until a subject is enrolled.

### **2.4.1 Inclusion Criteria**

- 2.4.1.1 The caregiver must have an eligible patient (defined in 2.4.1.5 – 2.4.1.9).
- 2.4.1.2 The caregiver must be of age  $\geq 18$  years.
- 2.4.1.3 The caregiver should be comfortable in reading and speaking English and signing informed consents.
- 2.4.1.4 The caregiver should provide at least 50% of care needs.
- 2.4.1.5 An eligible patient is one who identifies the eligible caregiver as their primary caregiver (i.e., provides at least 50% of care needs).
- 2.4.1.6 An eligible patient is age  $\geq 5$  years.
- 2.4.1.7 An eligible patient is scheduled to undergo HCT or recently had an HCT.
- 2.4.1.8 An eligible patient is able to sign informed consent/assent form or has an appropriate parent/guardian to sign on their behalf.
- 2.4.1.9 Patients and caregivers agree to provide informed consent that is in regulatory compliance and IRBMED-approved and also in accordance to institutional guidelines.
- 2.4.1.10 The caregiver and patient must have his/her own smartphone to participate.

### **2.4.2 Exclusion Criteria**

- 2.4.2.1 Patient does not meet eligibility criteria to undergo HCT at any participating site.

## 2.5 Intervention Plan

### 2.5.1 How will the intervention work?

Participants (caregiver-patient dyads) who are consented, enrolled, and randomized will be scheduled for a one-hour training session with the Research Coordinator(s) prior to or during admission to undergo the HCT. Based on our experience, these training sessions will be coordinated with other clinic appointments at the hospital in efforts to minimize burden on the caregiver and patient or remotely via institutionally approved virtual meeting platform. Once the intervention has begun, the Research Coordinator(s) will meet with the participants (caregiver-patient dyad) weekly to review any questions or concerns, to perform data download (wearable sensor device), and to ensure adherence to the protocol. HCT patients are typically inpatient for approximately four weeks. During this period, the Research Coordinator(s) will be available by pager and will schedule weekly visits with the participants or virtual visits. Once discharged, HCT patients return to clinic on a weekly visit in the ambulatory care setting. The Research Coordinator will meet with participants during those routine appointments. Roadmap 2.0 software will be maintained in collaboration with Arbormoon Software, Inc.

### 2.5.2 Intervention arm (Roadmap 2.0)

Participants (caregiver-patient dyads) randomized to the intervention arm will be instructed on how to download the wearable sensor app on their mobile phones or tablet (iOS, Android) and how to operate the wearable sensor. Each individual (caregiver, patient) will create her/his own password. The caregiver and patient will each receive a wearable sensor device (Fitbit).

University of Michigan inpatient only: Caregivers will be instructed on how to use the Roadmap 1.0 iPad. The Roadmap 1.0 iPad includes all of the features of Roadmap 1.0 components (see Table 1 of Section 1.8). After many rounds of discussion with HITS Compliance, it was deemed safest to maintain the previous components of Roadmap 1.0 in the inpatient setting (within the firewalls of Michigan Medicine due to privacy and security of patient-related data).

Caregivers will download the Roadmap 2.0 app onto their mobile phone or tablet (iOS, Android) to use it freely throughout inpatient and outpatient (intervention) period. Roadmap 2.0 contains no patient-related information. Timestamps will be recorded of each caregiver's use of Roadmap 1.0 and 2.0 (i.e., number of log-ins and pages viewed: when and how long and in what order). Please see **Appendix A** to view the components of Roadmap 1.0 and 2.0, and see **Appendix B** to view specifications of the wrist-worn sensor.

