**Treatment Description:**

The participants (caregiver-patient dyads) will be randomized to an active intervention arm (mobile platform + Positive Activities) or to a control arm (mobile platform + control). Blocked randomization will be used to limit bias and achieve an equal distribution of participants to the control and treatment arms. The study (intervention vs control) will be delivered from the time for admission of the patient's HCT through day 120 post-HCT. Participant data will be collected pre-intervention (baseline), during the intervention (day 30 post-HCT), and at the end of the intervention (day 120 post-HCT).

**Intervention arm (Positive Activities):** Caregivers and patients randomized to the treatment arm will be instructed on how to operate Roadmap 1.0 on an iPad (Michigan inpatients only) and Roadmap 2.0 (with Positive Activities for caregivers only) and Social Rhythms app on a mobile phone or tablet (inpatient and outpatient), download the app on the mobile device or tablet, be provided an access code, and to use Roadmap 2.0 with Positive Activities freely throughout the intervention period. The caregiver will receive a wearable sensor device (Fitbit); the patient will receive a wearable sensor device (Fitbit). The caregiver will download the Roadmap 2.0 app with Positive Activities, the patient will download the Roadmap 2.0 app without positive activities. Both the caregiver and patient will download the wearable sensor device (Fitbit) app onto their mobile phones or tablet. Both the caregiver and patient will download the Social Rhythms app and perform uploads at the survey intervals; baseline, day 30, and day 120.

**Control arm:** Participants will receive usual care only, defined as standard-of-care information provided according to institutional guidelines. The caregiver and patient will download the Roadmap 2.0 app without the Positive Activities and the caregiver and patient will also each receive a Fitbit device. Both caregiver and patient will download the wearable sensor device (Fitbit) app onto their mobile phones or tablet. Of note,

neither caregiver or patient in the control arm will receive Roadmap 1.0. Both the caregiver and patient will download the Social Rhythms app and perform uploads at the survey intervals; baseline, day 30, and day 120.

**Accrual Objective:** We will enroll a total of 300 caregiver-patient dyads (600 participants).

[figure not shown]

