#### ROADMAP 1.0 (Michigan Medicine only):

Caregiver iPad (inpatient only) \*

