## 1.8 Roadmap 1.0 Development

The app was developed on an iPad tablet as a multi-component mobile app to provide patient-specific information, education, and skills- building exercises for caregivers (**Table 1**). Patients, caregivers, and health care providers participated in *iterative cycles of user-centered design, development, and testing*. To date, >80 BMT caregivers have enrolled in IRB-approved studies to assess the feasibility of implementing BMT Roadmap. PROs were collected at baseline, discharge, and day 100. The most viewed modules were laboratory results and medications.

**Table 1.** BMT Roadmap Components

Patient-Specific Informational Resources	
Disease Characteristics	Infectious disease markers, blood type, donor type, donor characteristics, BMT regimen
Laboratory Studies	Results of laboratory studies updated in real-time
Medications	Medication list grouped according to indication (i.e. antibiotic, anti-emetic), dosing and schedule
Clinical Trials	Easy-to-read description of clinical trials and copies of consent
Provider Directory	Photos of healthcare providers in yearbook style
Patient-Specific Educational Resources	
Glossary	Commonly used words/terms and definitions used in the BMT journey
Phases of Care	Roadmap metaphor with detailed description of each phase of BMT
Symptoms/Side Effects	Description of commonly reported medication side effects
Patient-Specific Skills Building	
Videos	Video modules of central line care, dressing changes, cleaning, bathing
Discharge Checklist	Interactive list of 9-item discharge criteria to assess "Readiness"

[figure not shown]
**Roadmap 1.0 Use.** The app was rated highly useful and easy-to-use; caregiver anxiety decreased; caregiver well-being or HRQOL improved; and caregiver activation was increased at discharge compared with baseline. *Following memos and coding for content analyses*, major themes emerged, including: i) Roadmap usefulness, ease-of-use, and likeability; ii) positive aspects of caregiving (e.g., benefits); and iii) desire to expand BMT Roadmap directed to the caregiver with 'caregiver-specific resources' and 'positive activities' components (**Table 2**).

**Table 2.** Caregiver-Specific Resources and Positive Activities Components

Caregiver-Specific Resources	

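### At Michigan only the intervention arm gets the Roadmap 1.0 iPad, so a positive pooled primary result cannot by itself be credited to Roadmap 2.0

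*Combined protocol and SAP*

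**What the plan says.** **Who receives Roadmap 1.0.** Under the intervention arm, 2.5.2 states: "University of Michigan inpatient only: Caregivers will be instructed on how to use the Roadmap 1.0 iPad". The iPad carries every component in Table 1 of 1.8, including laboratory results, medication lists, education, skills videos and a discharge checklist. The study schema lists Roadmap 1.0 under the intervention arm for Michigan only and has no matching entry under control. The Synopsis, Treatment Description, says "neither caregiver or patient in the control arm will receive Roadmap 1.0".

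**What Roadmap 2.0 is.** Appendix B gives the treatment arm components A to D and the control arm component D alone. Roadmap 1.0 is not among A to D, and 2.5.2 treats 1.0 and 2.0 as separate tools with separately logged use.

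**What is claimed.** The primary hypothesis in 2.2 is that "a multi-component technology-mediated intervention (Roadmap 2.0) with focus on the positive aspects of caregiving will improve caregiver HRQOL". Sections 2.3.1 and 5.6 also name Roadmap 2.0 as the thing tested.

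**How it is analysed.** Randomization is stratified by transplant type only (5.4). Section 5.11 compares day 120 Global Health means by t-test or Wilcoxon test, adds regression on baseline caregiver characteristics, and analyses allo, auto and pediatric dyads separately. It names no breakdown by site.

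**The concern.** At Michigan, Roadmap 1.0 goes with the arm: the intervention arm has it and the control arm does not. No covariate can separate the two tools there. Elsewhere the arms differ only in Roadmap 2.0 content. The pooled difference mixes these contrasts in proportions set by how many dyads Michigan happens to enrol.

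Section 1.8 makes a Roadmap 1.0 contribution plausible. It reports better caregiver HRQOL, lower anxiety and higher activation at discharge than at baseline among users of that tool. If some of that carried through to day 120, a significant pooled result could be reported as evidence for Roadmap 2.0 when part of it belongs to a tool that other sites never had. The plan as written contains no analysis that would show this.

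**Working it through.** **1. The plan's own sample size, as the base for the illustrations.** Inputs from 5.7: effect 0.5 SD, SD 10 (so 5 points), two-sided alpha 0.05, power 0.80, 67 per arm. A two-sample t-test needs 63.8, i.e. 64 per arm, and has power 0.819 at 67. For the Wilcoxon test, dividing by its asymptotic relative efficiency of 3/π gives 63.77 / 0.955 = 66.8, i.e. 67 per arm, with power 0.801. The stated 67 is reproduced, and the steps below use it as the evaluable number per arm.

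**2. What the pooled difference estimates.** Let e2 be the Roadmap 2.0 effect (taken as equal at all sites), e1 the added effect of Roadmap 1.0 at day 120, and m Michigan's share of evaluable dyads (taken as equal in both arms).

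Pooled difference = (1 − m)·e2 + m·(e2 + e1) = e2 + m·e1

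The documents give neither e1 nor m. Assuming e1 from 0 to 3 points and m from 0 to 100%, the part due to Roadmap 1.0 runs from 0 × 0 = 0 to 1.0 × 3 = 3 points. At m = 100% there is one contrast and no averaging, but it is Roadmap 1.0 plus 2.0 throughout.

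**3. Chance of a significant pooled result if e2 = 0** (t-test, 67 per arm, SD 10, pooled effect m·e1):

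| e1 (assumed) | m = 25% | m = 50% | m = 75% | m = 100% |
|---|---|---|---|---|
| 0 points | 0.05 | 0.05 | 0.05 | 0.05 |
| 2 points | 0.06 | 0.09 | 0.14 | 0.21 |
| 3 points | 0.07 | 0.14 | 0.25 | 0.41 |

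Values above 0.05 are not a false-positive rate for the package, which truly works in those cells. They are the chance of a result that the present wording would credit to an inactive Roadmap 2.0.

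**4. What the other sites can show alone.** With n = 67·(1 − m) per arm, SE = 10·√(2/n) and an approximate 95% half-width of 1.96·SE:

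| m (assumed) | n per arm | SE | half-width | power for 5 points |
|---|---|---|---|---|
| 25% | 50.25 | 2.00 | 3.9 | 0.70 |
| 50% | 33.5 | 2.44 | 4.8 | 0.52 |
| 75% | 16.75 | 3.46 | 6.8 | 0.29 |

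**5. What an interaction test could show.** At m = 50% each site group has SE 2.44, so the difference between the two arm effects has SE 2.44 × √2 = 3.46. Power is about 0.14 for a true difference of 3 points and 0.06 for 1 point.

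**The case against.** **The package reading.** Section 1.8 reports a wish to expand BMT Roadmap, and the scientific premise in 1.9 speaks of expanding it and testing a multi-component intervention. Section 2.5.2 puts the iPad under the Roadmap 2.0 heading and says the older components stay inside the hospital firewall for privacy. Michigan could thus be seen as delivering one intended package on two devices. This shows that the arrangement is openly disclosed, but it does not settle the matter. If the intervention is 1.0 plus 2.0, the other sites do not deliver it; if it is 2.0, Michigan delivers something more. The privacy reason explains where the iPad is used, not why one arm lacks it.

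**Weak evidence of an effect at day 120.** This stands. The improvement in 1.8 was uncontrolled and measured at discharge, and the references attached to it concern a different caregiver quality-of-life instrument. The iPad is for inpatients, and 2.5.1 puts the stay at about four weeks, so use ends roughly three months before the endpoint. Zero belongs in the assumed range.

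**Partial cover in the plan.** Section 5.13.4 allows moderator-by-intervention interactions, and 2.5.2 logs Roadmap 1.0 use. Neither is tied to site, and use logged in one arm only cannot separate the tools.

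**Stronger inferences to avoid.** A reader might infer that the trial cannot say anything about Roadmap 2.0, or that its randomized comparison is biased. The documents support neither: the other sites isolate Roadmap 2.0, and the comparison of delivered packages is valid everywhere. A reader might also infer that Roadmap 1.0 must account for a material part of the 5-point target. That would need a floor on its effect and on Michigan's share, and the documents give neither.

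**Conclusion.** The concern holds as a problem of attribution. As 5.11 is written, a positive pooled result supports the package delivered at each site, and the Roadmap 2.0 wording in 2.2, 2.3.1 and 5.6 does not follow from it alone. The size is unknown: 0 to 3 T-score points of the pooled difference could come from Roadmap 1.0, on an assumed effect of 0 to 3 points, an assumed Michigan share of 0 to 100%, and a Roadmap 2.0 effect that is the same at all sites.

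The lack of site stratification is not the cause, and stratifying would leave the problem in place. A site main effect in the model would not help either, because within Michigan the two tools still coincide with arm.

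**What to change.** 1. **In 5.11**, prespecify the day 120 arm difference with its 95% CI separately for Michigan (labelled Roadmap 1.0 + 2.0) and the other sites (labelled Roadmap 2.0 alone). Do this first in the adult allo dyads, for which the trial is powered. The center ID described in 4.3 identifies the site. Report the difference between the two arm effects as an estimate with a CI, not as a decisive test, and note that the site groups are not randomized, so it may also reflect other differences between sites.
2. **In 2.2, 2.3.1 and 5.6**, describe the pooled contrast as the delivered package, and rest any claim about Roadmap 2.0 alone on the other-site estimate.
3. **Reconcile who uses Roadmap 1.0.** The Synopsis has both caregivers and patients instructed on it; the schema and 2.5.2 name caregivers only.

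The cost is SAP and protocol wording, with no new data and no change to what participants receive. The downside is an imprecise Roadmap 2.0-only estimate, as the working shows. Changing who receives Roadmap 1.0 partway through is not part of this fix: it would create a further Michigan contrast, and the documents do not say how far accrual has gone.

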### 2.5.3 Control arm

Participants randomized to the control arm will be instructed on how to download the Roadmap 2.0 (without Positive Activities) and wearable sensor app on their mobile phones or tablet (iOS, Android), and how to operate the wearable sensor. Each individual (caregiver, patient) will create her/his own password.

### 2.5.4 Wearable Sensor Device (Fitbit)

Each participant (caregiver, patient) will be given a wearable sensor to wear throughout the treatment period, except while in water or when charging. The goal is to collect objective, continuous, multi-parameter physiological data (e.g., total hours of sleep, sleep quality, total number of steps) on caregivers and patients throughout the treatment period to correlate with their subjective, snapshot caregiver- and patient-reported outcomes collected at three time points throughout the Intervention Period (baseline, and days 30 and 120 post-BMT). Participants will receive an instruction manual on how to charge and conveniently download data from the device. The data will be backed up to a HIPPA-secure data repository. For troubleshooting, detailed instructions will be provided for all participants, and customer support will be available 8AM – 5PM CST. Our team is available by pager after hours, if needed. Participants may use any Fitbit they may already have if they do not want to use the study provided Fitbit. Our study team will not be replacing any lost or broken Fitbit once a participant has reached Day 120 on study.

### 2.5.5 Social Rhythms App

Each participant will download the Social Rhythms app and upload their data at baseline (+/- 14 days), day 30 (+/- 14 days), and day 120 (+/- 30 days). At baseline, Social Rhythms will collect data starting 1 week prior to consenting. If a subject misses a Social Rhythms data upload, it will not be considered a study deviation. The Social Rhythms app is a tool developed by U-M investigators ([name] PhD) that provides information regarding one's circadian rhythm based on physiological data, which could inform how they organize their schedules. The Social Rhythms app collects data in a de-identified manner, we would be able to link our participants through a Fitbit identification number that is accounted for the Roadmap 2.0 app. We first debuted the Social Rhythms app in our study in University of Michigan students and COVID (HUM00185391). See **Appendix C** for details.

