#### Social Rhythms:

Both patient and caregiver will use this app to upload retroactive Fitbit data.

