#### **3.2 Exploratory Endpoints**

- 3.2.1 Caregiver HRQOL will be assessed by the PROMIS Global Health and Profile 29+2 scales at baseline (pre-intervention) and days 30 post-HCT.
- 3.2.2 Caregiver and patient HRQOL will be assessed by the PROMIS Companionship scale at baseline (pre-intervention), and days 30 and 120 post-HCT.
- 3.2.3 Caregiver and patient HRQOL will be assessed by the PROMIS Self-Efficacy for Managing Symptoms and Self-Efficacy for Managing Daily Activities scales at baseline (pre-intervention), and days 30 and 120 post-HCT.
- 3.2.4 Caregiver and patient HRQOL will be assessed by the PROMIS Positive Affect and Well-Being scale at baseline (pre-intervention), and days 30 and 120 post-HCT.
- 3.2.5 Caregiver and patient HRQOL will be assessed by the PROMIS Emotional Support at baseline (pre-intervention), and days 30 and 120 post-HCT.

- 3.2.6 Caregiver and patient HRQOL will be assessed by the Perceived Stress Scale at baseline (pre-intervention), and days 30 and 120 post-HCT.
- 3.2.7 Caregiver and patient HRQOL will be assessed by the Resilience, Optimism and Gratitude scales at baseline (pre-intervention), and days 30 and day 120 post-HCT.
- 3.2.8 Patient HRQOL will be assessed by the PROMIS Sleep Disturbance scale at baseline (pre-intervention), and days 30 and 120 post-HCT.
- 3.2.9 Caregiver and patient negative and positive dyadic interaction will be assessed by measures of the Dyadic Relationship Scale at baseline (pre-intervention), and days 30 and 120 post-HCT.
- 3.2.10 Caregiver HRQOL will be assessed by the TBI-CareQOL (PROMIS affiliate) Caregiver Anxiety at baseline (pre-intervention), and days 30 and 120 post-HCT.
- 3.2.11 Caregiver HRQOL will be assessed by the TBI-CareQOL (PROMIS affiliate) Caregiver Strain scale.
- 3.2.12 Activity data. Caregiver and patient activity (steps) and sleep will be measured continuously from the start to the end of the intervention (day 120 post-HCT) through wearable sensors.

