## APPENDIX C: SOCIAL RHYTHMS APP INTERFACE

Social rhythms is an app that collects data from either HealthKit on the app or Fitbit (health, sleep, and activity data). It uses this data to generate a report to the user about their circadian rhythm and supplies this report after a few days. The user can submit their data and obtain a report as frequently or little as they would like.

The report gives information on;

- Activity pattern: How your body's time clock has shifted due to the pandemic
- Regularity: Has your schedule become more or less regular during COVID
- Shift: Has your internal clock shifted to become earlier or later
- Sleep time: What time does your body start preparing for sleep
- Avoid light: What time should you begin to avoid bright light to avoid delaying your clock
- Light exposure: What time being exposed to light help you stay on track

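### The baseline Social Rhythms record starts a week before consent, which a study-issued Fitbit cannot cover, and no pre-admission wear is required

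*Combined protocol and SAP*

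**What the plan says.** **Baseline record.** Section 2.5.5 says "At baseline, Social Rhythms will collect data starting 1 week prior to consenting". It asks for uploads at baseline, day 30 and day 120, with a 14-day margin either side of baseline, but gives no calendar anchor for baseline. The arm descriptions in the study schema give the content of the upload: "Both patient and caregiver will use this app to upload retroactive Fitbit data". Section 3.2.15 also speaks of retroactive Fitbit data, and makes the upload voluntary. Appendix C is broader: the app "collects data from either HealthKit on the app or Fitbit".

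**Device timing.** Section 2.5.1 says that dyads "who are consented, enrolled, and randomized will be scheduled for a one-hour training session with the Research Coordinator(s) prior to or during admission". Sections 2.5.2 and 2.5.3 describe sensor set-up for participants already randomized. The Time and Events Table marks sensor training only in the pre-admission column. Section 4.5 limits randomization to at most 21 days before planned conditioning.

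**Capture period.** Section 2.5.4 has the device worn during the treatment period and lets participants use a Fitbit of their own. Section 3.2.12 says that steps and "sleep will be measured continuously from the start to the end of the intervention (day 120 post-HCT) through wearable sensors". The synopsis starts the intervention at admission.

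**Analysis.** Section 5.13.5 compares the derived sensor variables between arms and mentions no baseline. Section 5.13.2 does adjust patient-reported outcomes for baseline scores.

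**The concern.** The baseline record is defined to begin on days when the study device is not yet in the participant's hands. Whether the pre-consent week exists then depends on owning a Fitbit or having a phone health record beforehand, which the trial neither controls nor requires.

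The protocol's own purposes make some reference period useful. Section 2.5.4 wants sensor data to set against patient-reported outcomes at baseline, day 30 and day 120, and the baseline questionnaire is taken before the intervention. No matching sensor window is defined. Admission and conditioning can be expected to disturb steps, sleep and rhythm, so days recorded after admission are a poor substitute.

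Two things are at stake: a baseline record whose completeness depends on prior device ownership, and precision given up in the between-arm sensor comparisons. Both concern exploratory endpoints.

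**Working it through.** The plan gives no figure on this point to reproduce. The check sets dates and data sources side by side and then sizes what can be sized.

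**1. Can the study Fitbit cover the pre-consent week?** Consent comes first, then enrolment and randomization, then training (2.5.1). Set-up is described only for randomized participants (2.5.2, 2.5.3). That device is issued after consent is inferred from these sections and the Time and Events Table; no single sentence says so. On that order, a study-issued Fitbit holds 0 of the 7 days.

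**2. Who can supply the week?** Owners of a Fitbit (2.5.4), and users with HealthKit data (Appendix C). Both routes have gaps. Section 2.5.5 links records by a Fitbit identification number, and no linkage is given for a HealthKit-only record. Appendix A has coordinators create study accounts, without saying how an owner's earlier data would reach them.

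**3. How many cannot?** Let q be the share of the 600 participants with a usable own record. The number without one is 600 × (1 − q). The caregiver and patient questionnaires in Appendix D ask about device ownership, but no rate is given or assumed, so q is varied:

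| Assumed q | Participants without the pre-consent week |
|---|---|
| 0% | 600 × 1.00 = 600 |
| 10% | 600 × 0.90 = 540 |
| 25% | 600 × 0.75 = 450 |
| 50% | 600 × 0.50 = 300 |
| 75% | 600 × 0.25 = 150 |

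**4. Is there a pre-intervention period after consent?** There can be. Training may fall "prior to or during admission to undergo the HCT", and the intervention starts at admission.
- Lower end: training during admission gives 0 days.
- Upper end: issue immediately after randomization, with admission assumed near the start of conditioning, gives about 21 days (4.5).

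No section requires or defines wear in this interval.

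**5. What would a usable baseline add?** With baseline and follow-up correlated r within person, adjustment reduces residual variance by r². The documents give no r, so these values are assumptions:
- r = 0.3: 0.3² = 9%
- r = 0.5: 0.5² = 25%
- r = 0.7: 0.7² = 49%

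These reductions apply to participants who have a baseline; the overall gain is smaller when some do not.

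**The case against.** The strongest reply has four parts.

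**Pre-consent is not pre-intervention.** A reader might infer that most participants have no pre-intervention sensor baseline. The documents do not support that. More than half would lack the pre-consent week only if q were below 50%, and q is not given. Even those participants may have days between consent and admission. Section 2.5.5 fixes where the record starts, not where it ends, so days worn before the baseline upload could count. This part stands. What remains is that such days are possible but not required.

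**Randomization protects the comparison.** A reader might also infer that the arm comparisons in 5.13.5 are biased for want of a baseline. They are not: an unadjusted randomized comparison does not need one. The plan also specifies no change-from-baseline analysis for sensor data. This stands, so the cost in the arm comparison is precision alone.

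**The precision gain may be small.** If admission and conditioning disrupt activity and sleep strongly, a pre-admission week may predict later values poorly. This is fair, and is why the range extends down to r = 0.3.

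**A change of data source is not inevitable.** Fitbit owners may keep their own device throughout (2.5.4). A change arises only for those who start with HealthKit or their own Fitbit and move to the study device.

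The stakes are also low: uploads are encouraged rather than mandatory, and 2.5.5 does not count a missed one as a deviation. None of this removes the conflict between 2.5.5 and the device timing.

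**Conclusion.** The concern holds as a conflict between sections that should be reconciled. Participants who depend on the study-issued Fitbit cannot provide the pre-consent week that 2.5.5 names. Any other sensor baseline is left to chance, at 0 to about 21 days. The number affected cannot be stated from the documents.

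The conclusion rests on device issue following consent, which is a sound inference from 2.5.1 to 2.5.3 and the Time and Events Table. The 21-day upper end assumes admission close to the start of conditioning. The 9% to 49% range rests wholly on assumed correlations.

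The consequence is confined to the exploratory activity, sleep and circadian endpoints. The primary endpoint, caregiver Global Health at day 120, and its sample size do not depend on it.

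**What to change.** - **Sections 2.5.5 and 3.2.12:** define the sensor and Social Rhythms baseline as the available days of Fitbit wear after consent and before admission, up to 7. The device may be study-issued or the participant's own, preferably the same one throughout.
- **Device issue:** issue and pair the Fitbit as soon after consent as feasible. Reconcile the Time and Events Table, 2.5.1 to 2.5.5, 3.2.12, 3.2.15 and Appendix C on when the device is set up, when capture starts and which source is used.
- **Pre-consent data:** treat own-Fitbit or HealthKit data from before consent as supplementary description.
- **Section 5.13.5:** compare steps and sleep between arms adjusted for this baseline where available, keeping participants without one in the analysis by a rule stated in advance. Report baseline days available by arm.

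One caution applies. The Time and Events Table puts Roadmap 2.0 training and download before admission, so some baseline days may follow first use of the Positive Activities. The usage timestamps in 2.5.2 allow this to be checked, and such days could be left out in a sensitivity analysis. The synopsis states a delivery period; it does not say that the activities are locked until admission, and this fix does not require that.

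The cost is protocol wording and earlier hand-out of a device already supplied. Because consent is electronic (4.3) and training may be remote (2.5.1), some sites may need to arrange shipment. Recruitment runs close to admission (4.1), and patients already transplanted are eligible (2.4.1.7), so dyads enrolled at or after admission will have a short or missing baseline. The plan should say so.
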